1.0 OBJECTIVES

1.1 Primary Objective

- To explore the efficacy of combining stereotactic body radiotherapy (SBRT) with FLT3 ligand immunotherapy for advanced non-small cell lung cancer (NSCLC) and for other advanced solid tumors after treatment with immune checkpoint inhibitors targeting the PD-1/PD-L1 axis.

1.2 Secondary Objectives

- To establish the feasibility and safety of combining SBRT with FLT3 ligand immunotherapy for advanced NSCLC and for other advanced solid tumors after treatment with immune checkpoint inhibitors targeting the PD-1/PD-L1 axis.
- To quantify and evaluate potential surrogate outcomes for clinical efficacy of this treatment approach, including radiographic responses, immunologic responses, and circulating tumor cell levels.

2.0 BACKGROUND

2.1 Non-Small Cell Lung Cancer

Non-small cell lung cancer (NSCLC) is the leading cause of cancer mortality in the United States and worldwide, causing nearly one million deaths each year.[1] For the approximately 40% of NSCLC patients who present with stage IV disease and other patients who progress after presenting with localized disease, standard first-line therapy typically consists of combination chemotherapy, usually with a platinum doublet. Median progression-free survival (PFS) for such patients is on the order of 6 months.[2, 3] Second-line systemic therapy, when it can be delivered, yields even poorer outcomes, with median PFS durations of approximately 3 months.[4, 5] While targeted therapy clearly improves outcomes for the minority of patients with identifiable driver mutations, novel strategies to improve outcomes for the remainder of advanced NSCLC patients are sorely needed.

Cancer immunotherapy, which refers to treatment strategies that induce the patient's own immune system to attack tumor cells, is an emerging tool in the oncologist's armamentarium. Sipuleucel-T, a therapeutic vaccine for prostate cancer, gained FDA approved for the treatment of metastatic, hormone refractory prostate cancer in 2010. Ipilimumab, a monoclonal antibody to CTLA-4 that promotes cancer cell killing by cytotoxic T lymphocytes, was approved for the treatment of advanced melanoma in 2011. Pembrolizumab and nivolumab, which both blocks the protein programmed cell death 1 (PD-1) from binding its ligands PD-L1 and PD-L2 to permit cytotoxic T cell activation, were both approved by the FDA for the treatment of advanced melanoma in 2014. Although several groups are exploring methods to utilize the immune system to fight lung cancer, the use of immunotherapy for NSCLC remains largely investigational at this point.[6-8] Of note, nivolumab gained approval for the second-line treatment of advanced squamous NSCLC in March 2015 after demonstrating an overall survival benefit (median 9 months versus 6 months) when compared to docetaxel in a randomized multicenter trial.

Our group and others have demonstrated that ionizing radiotherapy (RT) has the potential to enhance the effectiveness of cancer immunotherapy. RT may serve to amplify the tumor-specific peptide repertoire and upregulate cell surface expression of MHC determinants and costimulatory molecules. [9, 10] RT may also evoke changes in the tumor microenvironment that facilitate the host immune response.[11, 12] We believe that RT is a key to unlocking the potential of immunotherapy as an effective approach in the treatment of NSCLC.

2.2 FLT3 Ligand

Fms-like tyrosine kinase 3 (FLT3) ligand is a potent hematopoietic growth factor that mobilizes stem cells and greatly increases the number of circulating dendritic cells (DCs) in blood and organs.[13] FLT3 ligand has been shown to evoke immune responses and cause tumor regression in animal models of fibrosarcoma, breast cancer, prostate cancer, and lung adenocarcinoma.[14-17]

Amgen's recombinant human FLT3L, AMG949, has been studied in numerous industry and investigator-initiated clinical trials. Collectively, approximately 150 healthy volunteers and 380 cancer patients were enrolled on those trials. Adverse events requiring cessation of treatment were rare (<5%). However, FLT3L did not demonstrate definitive anti-tumor activity in patients with ovarian cancer, breast cancer, or non-Hodgkin's lymphoma. This may have been related to the immobilization of immature DCs by FLT3 or limited DC access to tumor antigens.

Celldex Pharmaceuticals has developed a new FLT3L (CDX-301). CDX-301 is produced using a serum-free manufacturing process, and it is identical in amino acid sequence to AMG949. A phase I study using 30 healthy volunteers has been completed, and no major toxicities were observed. (See Section 7.2 for further details) DC expansion has been shown to peak approximately two weeks after initiation of FLT3 ligand therapy (Figure 1). Based on promising data from our laboratory demonstrating synergy between ablative local RT and FLT3 ligand immunotherapy in murine NSCLC models (summarized below), our first clinical trials in this arena will test the combination of CDX-301 and SBRT for advanced NSCLC.

[figure not shown]

Figure 1 – Expansion of two dendritic cell populations in healthy volunteers treated with CDX-301 peaks at 10-14 days after treatment initiation. (source: Celldex Therapeutics)

2.3 Stereotactic Body Radiotherapy

In recent years, hypofractionated stereotactic body radiotherapy (SBRT) has emerged as an effective treatment option for numerous malignancies. SBRT uses the principles of intracranial stereotactic radiosurgery (large daily doses delivered precisely to a small target volume over a short treatment course) to treat extracranial disease sites. For stage I NSCLC, SBRT has demonstrated excellent local control rates. [18-20] Increased utilization of SBRT has been linked to improvements in overall survival. [21] Serious adverse events following SBRT for NSCLC are very rare[22], except when aggressive SBRT regimens are used to treat central lesions. [23] Importantly, the highly-conformal manner in which SBRT is delivered allows safe treatment of lung tumors in patients with poor pulmonary function.[24] SBRT has also been shown to be safe in extrathoracic disease sites such as the liver and spine.[25, 26]

A wide variety of dosing and fractionation schedules has been used to deliver lung SBRT for NSCLC.[19, 20] Although there is evidence of a dose-response relationship when relatively low-dose regimens (BED < 100 Gy) are used,[19, 20] more intense regimens have yielded consistently excellent results and are considered to be ablative. These include 10-12.5 Gy x 4-5 fractions, 18-20 Gy x 3 fractions, and 25-34 Gy in a single fraction. A randomized RTOG study demonstrated that 34 Gy x 1 fraction is a safe and effective regimen for peripheral tumors.[27] This single fraction dose will be the new standard for the treatment of peripheral lesions in upcoming RTOG SBRT trials. For central lesions, less aggressive regimens such as 10-12 Gy x 5 are recommended. The National Comprehensive Cancer Network (NCCN) now provides guidelines for the selection of an SBRT schedule as well as dosimetric constraints that should be met for each organ at risk and course length:

Table 2. Commonly Used Doses for SABR

Total Dose	# Fractions	Example Indications
25-34 Gy	1	Peripheral, small (<2 cm) tumors, esp. >1 cm from chest wall
45-60 Gy	3	Peripheral tumors and >1 cm from chest wall
48-50 Gy	4	Central or peripheral tumors <4-5 cm, especially <1 cm from chest wall
50-55 Gy	5	Central or peripheral tumors, especially <1 cm from chest wall
60-70 Gy	8-10	Central tumors

Table 3. Maximum Dose Constraints for SABR*

OAR/Regimen	1 Fraction	3 Fractions	4 Fractions	5 Fractions
Spinal Cord	14 Gy	18 Gy (6 Gy/fx)	26 Gy (6.5 Gy/fx)	30 Gy (6 Gy/fx)
Esophagus	15.4 Gy	30 Gy (10 Gy/fx)	30 Gy (7.5 Gy/fx)	32.5 Gy (6.5 Gy/fx)
Brachial Plexus	17.5 Gy	21 Gy (7 Gy/fx)	27.2 Gy (6.8 Gy/fx)	30 Gy (6 Gy/fx)
Heart/Pericardium	22 Gy	30 Gy (10 Gy/fx)	34 Gy (8.5 Gy/fx)	35 Gy (7 Gy/fx)
Great Vessels	37 Gy	39 Gy (13 Gy/fx)	49 Gy (12.25 Gy/fx)	55 Gy (11 Gy/fx)
Trachea & Proximal Bronchi	20.2 Gy	30 Gy (10 Gy/fx)	34.8 Gy (8.7 Gy/fx)	32.5 Gy (6.5 Gy/fx)
Rib	30 Gy	30 Gy (10 Gy/fx)	30 Gy (7.5 Gy/fx)	32.5 Gy (6.5 Gy/fx)
Skin	26 Gy	30 Gy (10 Gy/fx)	36 Gy (9 Gy/fx)	40 Gy (8 Gy/fx)
Stomach	12.4 Gy	27 Gy (9 Gy/fx)	30 Gy (7.5 Gy/fx)	35 Gy (7 Gy/fx)

*Based on constraints used in recent and ongoing RTOG SABR trials (RTOG 0618, 0813, & 0915).

SBRT is now often used to treat primary tumors and metastases in sites outside the lung, both for NSCLC and for other malignancies. Techniques to safely deliver

SBRT to the skeleton, abdomen, pelvis, and extremities have been established[28]. SBRT for patients with limited metastatic disease may become a standard approach based on recently completed[29, 30] and ongoing randomized trials.

2.4 FLT3 Ligand and Radiotherapy

Published laboratory results from our department demonstrate that pretreatment of a single lesion with high-dose RT increases the systemic efficacy of FLT3 ligand in a murine model of lung adenocarcinoma. [14] Mice with established, 3-week-old Lewis lung tumors were given a single dose of localized primary footpad tumor RT (60 Gy), with or without FLT3 ligand (administered daily for 10 days after RT). The combination of RT and FLT3 ligand significantly increased survival compared to either treatment alone and compared to controls (Figure 2). Examination of animal lung tissue revealed that the lungs of mice treated with RT and FLT3 ligand showed no carcinoma cells but had infiltrates of neutrophils, lymphocytes, and mononuclear leukocytes. Lungs from other cohorts demonstrated massive tumor cell infiltration. (Figure 3)

[figure not shown]

Figure 2 – Local RT acts synergistically with FLT3 ligand in a murine NSCLC model to improve overall survival.

[figure not shown]

Figure 3 – Murine lungs following treatment with RT plus FLT3 ligand demonstrate leukocytic infiltrates without tumor cells (left), compared to tumor-laden lungs of mice from other cohorts (right).

We recently obtained similar results in a newer, unpublished experiment using the Celldex FLT3 ligand CDX-301. (Figures 4 and 5) Again, in a murine adenocarcinoma model, combination therapy with RT and FLT3 ligand improved overall survival compared to either treatment alone. In this case, the dose of 60 Gy was divided into three fractions to mimic an SBRT schedule commonly employed in NSCLC patients. Poorer outcomes were seen in the combination therapy arm compared to that in the prior study, likely because surviving mice were re-challenged with tumor cells eight weeks after completion of immunotherapy. We hypothesize that additional cycles of FLT3 ligand, possibly in combination with repeat irradiation of viable lesions, might prolong treatment efficacy.

[figure not shown]

Figure 4 – Design for murine study of FLT3 ligand (CDX-301) and hypofractionated RT.

[figure not shown]

Figure 5 – Murine survival curves. Log-rank testing of the combination therapy arm against each monotherapy arm yields p-values of 0.04.

The data summarized above indicate that the combination of SBRT to a pulmonary or metastatic NSCLC lesion and CDX-301 is likely to be well-tolerated and may have significant clinical activity in advanced NSCLC patients. The study described herein will be the first clinical trial to test this approach.

Figure 7 – Kaplan-Meier curves for overall survival and progression-free survival for the first 9 study subjects

Based on these exciting results, which were presented at the Clinical Trials Plenary Session at the 2018 AACR Annual Meeting, we are adding a second study cohort to this protocol. This group will include patients with advanced solid tumors other than NSCLC who have previously been treated with immune checkpoint therapy targeting the PD-1/PD-L1 axis.

3.0 PATIENT ELIGIBILITY

3.1 Inclusion Criteria

- Cohort 1: AJCC stage 3 or 4 histologically proven NSCLC not amenable to curative therapy
- Cohort 2: Advanced solid (excluding lymphomas and leukemias) malignancy other than NSCLC not amenable to curative therapy and previously treated with immune checkpoint therapy targeting the PD-1/PD-L1 axis with an agent approved by the FDA for that setting.
- Age \geq 18 years
- Prior treatment with at least one standard chemotherapy regimen or targeted agent prior to enrollment
- Radiological assessment within 21 days prior to study entry demonstrating measurable disease that includes at least one pulmonary or extrapulmonary lesion \geq 1 cm in greatest dimension that would be amenable to SBRT and at least one measurable lesion that would be outside of the SBRT treatment fields
- History/physical examination within 30 days prior to registration
- ECOG performance status 0-2
- Signed, written informed consent

3.2 Exclusion Criteria

- Less than 21 days between registration and the last receipt of chemotherapy, biotherapy, immunotherapy, radiotherapy (excluding palliative radiotherapy), or major surgery. Prior receipt of immunomodulatory therapy (e.g.: nivolumab) is permitted, as long as there has been a 21-day washout period following the most recent treatment.
- Untreated central nervous system metastases. Patients with a history of brain metastases must have had no CNS-directed therapy within the past 60 days and radiological assessment within 30 days of study entry demonstrating a lack of progressive CNS disease
- Ongoing or recent (within 21 days prior to study entry) use of high dose oral corticosteroids (≥ 2 mg of dexamethasone daily or equivalent). Intranasal and/or inhaled corticosteroid use is permitted.
- Any unresolved CTCAE grade > 2 toxicity from previous anti-cancer therapy. Patients with irreversible toxicity that is not reasonably expected to be exacerbated by study therapy (e.g., hearing loss) may be enrolled after discussion with the principal investigators.
- History of allogeneic organ transplant or autoimmune disease
- Other active malignancy for which systemic therapy is indicated. History of adequately treated local basal cell or squamous cell carcinoma of the skin, cervical carcinoma in situ, superficial bladder cancer, asymptomatic prostate cancer without known metastatic disease and with no requirement for therapy besides from hormonal therapy, adequately treated stage 1 or 2 cancer currently in complete remission, or any other cancer that has been in complete remission for ≥ 5 years is permitted.
- Uncontrolled intercurrent illness including, but not limited to, symptomatic congestive heart failure, unstable angina pectoris, uncontrolled cardiac arrhythmia, or psychiatric illness/social situation that would limit compliance with study requirements as judged by the treating physicians
- The following laboratory results, within 10 days of first study drug administration:
 - Hemoglobin ≤ 9.0 g/dL, Absolute neutrophil count $\leq 1.5 \times 10^9/L$, Platelet count $\leq 100 \times 10^9/L$
 - Serum creatinine $\geq 1.5 \times$ ULN and creatinine clearance (by Cockcroft-Gault formula) < 60 mL/min
- Women of child bearing potential: positive pregnancy test (serum)

4.0 STUDY DESIGN

4.1 General Design

This is a single-arm, phase II study with two cohorts. A total of 29 patients will be enrolled in Cohort 1, and 20 patients will be enrolled in Cohort 2. All patients will be treated with SBRT to a single pulmonary or extrapulmonary lesion as well as FLT3 ligand immunotherapy. Patients will be followed closely for the development of any

treatment-related toxicities. Whole-body PET/CT imaging will be performed prior to study entry and every 8 weeks thereafter.

4.2 Study Calendar

	Pre-rx	Week 1	Week 2	Week 3	Week 4	Week 5	Week 6	Week 7	Week 8	Weeks 16, 24, 32
Stereotactic Radiotherapy (SBRT)		X X X								
FLT3 Ligand Therapy		XXXXX								
History and Physical Examination	X	X	X	X	X		X		X	X
Blood Tests: CBC, CMP	X	X	X	X	X		X		X	X
PET/CT	X								X	X
Immune Correlates	X		X		X				X	X

Additional cycles of SBRT and FLT3 ligand may be administered after 8 weeks or more in cases where treatment is well-tolerated and seems to provide clinical benefit, at the discretion of the treating physicians. In addition to the time points specified above, blood samples for immune correlates will also be drawn at the first clinic visit following disease progression. Immune correlates will include anti-drug antibody testing for CDX-301, which will be performed by sending study samples to Celldex. For diseases where PET/CT is not commonly used (e.g., hepatocellular carcinoma), PET/CT may be replaced by CT and/or MRI.

4.3 Primary Endpoint

- The primary endpoint is progression-free survival rate at four months (PFS4), defined as the rate estimate of the percentage of patients who are alive and progression-free at 16 weeks (~4 months) after initiation of study therapy.

4.4 Secondary Endpoints

- Dose limiting toxicities (DLTs): For the purposes of this study, a DLT will be defined as any treatment-emergent grade 3-5 toxicity, scored using the Common Terminology Criteria for Adverse Events (CTCAE) version 4.0, and occurring within 30 days after treatment with SBRT in combination with FLT3 ligand therapy. Asymptomatic laboratory abnormalities (e.g.: leukocytosis) that do not require intervention will not be counted as DLTs. For subjects who receive more than one “cycle” of SBRT and FLT3 ligand, only adverse events that occur after the first cycle will be scored as potential DLTs.
- Clinical/radiographic endpoints: These will include radiographic response rates, disease progression, and death. Radiographic endpoints will be scored using according to immune-related response criteria (irRC).[31] To allow comparison of our data with historical experiences, we will also score radiographic findings using RECIST 1.1 criteria.[32] Pre- and post-treatment assessments will include PET/CT imaging, so that we can assess responses using PERCIST criteria[33] and with volumetric PET measures, which have been shown to be prognostic in metastatic NSCLC patients [34, 35] and predictive of clinical outcomes in advanced NSCLC patients treated with targeted therapy.[36] SBRT target lesions will not be considered in the radiographic evaluation of treatment responses, as rates of treatment response and disease control in lesions treated

with SBRT have been shown to be excellent and may not be indicative of the effectiveness of combined modality therapy.

- Potential surrogate outcomes for clinical endpoints: We will collect plasma samples at regular intervals to facilitate monitoring immune responses such as DC expansion. We will also follow T-cell inducible costimulator (ICOS) expression. ICOS is a member of the immunoglobulin superfamily. Responses to immunotherapy have been associated with increased ICOS expression on CD8+ T-cells, particularly following CTLA-4 blockade.[37-40] We will follow serum levels of high-mobility group box 1 (HMGB1), whose release has been linked to antitumor immune responses.[41, 42] Flow cytometry will be performed to track measures of DC maturation such as CD83 and CD86 expression.[43] Other correlative studies will be performed in collaboration with [name] laboratory and the study sponsor.

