5.2 FLT3 Ligand Therapy (CDX-301)

- Daily subcutaneous injections of CDX-301 (75 µg/kg) will be administered for 5 days, beginning on the first day of SBRT.
- Additional “cycles” of SBRT (to distinct lesions) and CDX-301 may be administered every 2-4 months to subjects who demonstrate evidence of clinical benefit (lack of treatment-related toxicity and no disease progression).
- Study therapy will be discontinued in cases of treatment-related toxicity or disease progression.

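### Does PFS4 lack a rule for irradiated lesions, in particular those given SBRT between week 8 and the week-16 scan?

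*Combined protocol and SAP*

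**What the plan says.** Section 4.3 defines PFS4 as the proportion alive and without progression 16 weeks after study therapy starts. Section 6.1 adds the Cohort 1 rule: success if at least 10 of 29 patients meet that definition, with a null rate of 20% and an alternative of 40.5%. Neither section says which lesions count towards progression.

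The only lesion rule is in the clinical/radiographic bullet of section 4.4. On the endpoints in that bullet it says: "These will include radiographic response rates, disease progression, and death". It names irRC, with RECIST 1.1 alongside, and then states that "SBRT target lesions will not be considered in the radiographic evaluation of treatment responses". The reason given is that "rates of treatment response and disease control in lesions treated" with SBRT are already known to be excellent and may say little about the combination.

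On later cycles, section 4.2 says: "Additional cycles of SBRT and FLT3 ligand may be administered after 8 weeks or more". Section 5.2 says that "SBRT (to distinct lesions) and CDX-301 may be administered every 2-4 months", for patients with clinical benefit, which it defines as no treatment-related toxicity and no progression. The DLT bullet in 4.4 does carry a cycle limit: "only adverse events that occur after the first cycle will be scored as potential DLTs". Section 3.1 requires at least one measurable lesion outside the SBRT fields at entry. Section 6.3 bases response rates on the first scan after treatment.

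**The concern.** The exclusion sits under secondary endpoints and is worded for responses, while the primary endpoint is about progression. A literal reader could hold that it does not reach PFS4, so that irradiated lesions count there. The question arises for every patient, because all receive SBRT to one lesion in the first cycle.

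Later cycles add to it. A lesion measured at baseline and week 8 may be irradiated before the week-16 scan. If it is left out, its growth cannot count as progression. If it is kept, its shrinkage may mask growth elsewhere. A patient who entered with a single lesion outside the first field could reach week 16 with no unirradiated measurable lesion. Repeat treatment is no remote possibility: section 2.4 suggests that more FLT3 ligand, "possibly in combination with repeat irradiation of viable lesions, might prolong treatment efficacy".

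The trial has one arm, and section 2.5 already shows "Kaplan-Meier curves for overall survival and progression-free survival for the first 9 study subjects". If the scoring rule really were open, it could be chosen with outcomes in view, and one patient can decide whether 10 of 29 is reached.

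**Working it through.** **1. The plan's own figures.** Inputs from section 6.1: n = 29, cut-off 10, p0 = 0.20, p1 = 0.405. With X the number of successes, X ~ Bin(29, p):

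| Cut-off | P(X ≥ cut-off) at 0.20 | P(X ≥ cut-off) at 0.405 |
|---|---|---|
| 9 | 10.84% | 89.17% |
| **10 (plan)** | **4.93%** | **80.09%** |
| 11 | 1.97% | 67.73% |

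The stated limits (at most 5%, at least 80%) are met.

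**2. Leverage of one patient.** One patient is 1/29 = 3.4 percentage points. One reclassification matters when the count is 9 or 10:
- at 20%: P(9) + P(10) = (10.84 − 4.93) + (4.93 − 1.97) = 5.91 + 2.96 = 8.87%;
- at 40.5%: (89.17 − 80.09) + (80.09 − 67.73) = 9.08 + 12.36 = 21.44%.

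This describes the cut-off. It says nothing about how often re-irradiation would change a score, and it would apply equally to any doubt about the endpoint.

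**3. Can the two readings differ?** Assume two lesions of 2.0 each, one irradiated in cycle 2, and progression judged on the change in summed size. The documents give neither the sizes nor the summing rule, so both are assumptions.
- Irradiated lesion −30%, other +40%. Kept: (1.4 + 2.8)/4.0 = 1.05, or +5%. Left out: 2.8/2.0 = 1.40, or +40%.
- Irradiated lesion +60%, other unchanged. Kept: (3.2 + 2.0)/4.0 = 1.30, or +30%. Left out: 2.0/2.0 = 1.00, or 0%.

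The readings can disagree, in either direction. The second case needs marked growth in an irradiated lesion, which 4.4 expects to be uncommon.

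**4. Is the rule really open?** Three features of section 4.4 point the same way.
- The bullet is about radiographic endpoints as a group and lists progression among them.
- The stated reason covers disease control as well as response. Control of an irradiated lesion bears on progression.
- The term for the excluded lesions has no cycle attached, while the DLT bullet in the same section has an explicit first-cycle limit. The authors wrote a limit where they wanted one.

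No other section gives a competing lesion rule. Section 3.1's demand for a measurable lesion outside the fields also fits an assessment made on unirradiated disease.

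**5. How wide is the exposed window for later cycles?** Section 4.2 opens it at week 8, and the PFS4 reading at week 16 closes it: 16 − 8 = 8 weeks. A cycle at the 4-month end of 5.2's spacing falls at about week 16 or later. Re-treatment requires no progression, so it cannot undo an event already recorded. Death still counts under 4.3, and growth in any unirradiated lesion still counts on either reading. Response rates are normally untouched, because the first post-treatment scan is at week 8. To be affected, a patient must be progression-free, be re-treated early in the spacing, and have a week-16 status that turns on the re-treated lesion.

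**The case for a change.** The strongest counter-argument is that a primary endpoint should not have to be inferred from a secondary-endpoint bullet that speaks of responses, least of all in a single-arm trial with PFS already presented for 9 subjects. The cut-off has little slack. If a share m of patients who had progressed were scored progression-free, the type I error at a true 20% would be evaluated at 0.20 + 0.80m: 6.2% for m = 1% (0.208) and 13.6% for m = 5% (0.24). In the other direction, if 5% of progression-free patients were scored as progressed, power would fall from 80.1% to 73.3% (0.405 × 0.95 = 0.385). One sentence would remove the doubt.

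Part of this stands. Sections 4.3 and 6.1 contain no pointer to 4.4, the wording leaves some doubt, and the case of a patient with no unirradiated measurable lesion at week 16 is not discussed. But the values of m are assumptions with no support in the documents. They also presuppose that leaving the lesion out is an error, whereas on the natural reading that is the endpoint's definition. The argument does not show that following the plan gives a wrong answer. It favours neither reading, because each has a cost: one loses growth in an irradiated lesion as an event, and the other brings into PFS4 the local SBRT effect that 4.4 sets aside. Counting how many successes had further SBRT before week 16 would be useful description, but it changes no result. Most of section 2.5 was not available for this review, so how PFS was scored in the reported subjects cannot be held against the plan.

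**Conclusion.** The concern does not call for a change. The calculations are correct and the missing cross-reference is real, but it is not accurate to say that PFS4 has no rule. Section 4.4 gives one that reads naturally as covering progression and lesions irradiated in any cycle, and an analyst would apply it that way. What remains is a low-severity gap in wording. For later cycles it is confined to lesions irradiated in the roughly 8 weeks before the week-16 scan, in patients who had not progressed.

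Its effect on PFS4 cannot be sized from the documents: they give no number of re-treated patients, no lesion data and no direction. The 8.9% and 21.4% chances of a count of 9 or 10 are properties of the 10-of-29 rule. Spelling out the choice would leave n = 29, the cut-off of 10, the 4.93% type I error and the 80.1% power unchanged. The conclusion rests on reading the exclusion with its own bullet and its stated reason, and on section 5.2's condition that patients are progression-free when re-treated.
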